### 3.2 Rationale for Study Design and Control Group

This study was designed to be consistent with the US FDA Guidance for Industry on Providing Clinical Evidence of Effectiveness for Human Drug and Biological Products, with the ICH, Guidance on The Extent of Population Exposure to Assess Clinical Safety for Drugs Intended for Long-Term Treatment of Non-Life-Threatening Conditions and with the ethical principles given in these guidances, which have their origins in the Declaration of Helsinki. The inclusion of a placebo as a control into sequences A and B in the Treatment Phase of this study is necessary to determine the efficacy and safety of this new investigational medicinal product. Inclusion of the placebo sequence C will preserve blinding. A crossover design has been selected in order to evaluate the safety, tolerability, and effects on excessive sleepiness across a range of doses. Phase 2 studies in patients with narcolepsy have shown that JZP-110 (150 and 300 mg doses) improves subjective and objective parameters of sleepiness and is well tolerated. While the same sleepiness parameters are included as endpoints in this study as in the Phase 2 narcolepsy study, the objective MWT assessment was made optional in Amendment 2 for this study as unlike in narcolepsy, it is not a common assessment for diagnosing sleepiness in PD and it has not been validated in this patient population. The Phase 2a narcolepsy study was a crossover design and a carryover effect was not observed. In light of this and the short half-life of JZP-110, a placebo washout between each treatment period was not included. The doses of 75, 150 and 300 mg selected for evaluation in this study are comparable to those currently being evaluated in ongoing Phase 3 studies in the OSA and narcolepsy populations. It is feasible that lower doses may be pharmacologically active and therefore, a broad range of doses from 75 to 300 mg given once daily for 7 days

was selected for evaluation and will provide useful data to inform dose selection for subsequent studies.

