**Table 1 Overview of Study Treatment Sequences by Treatment Period**

Treatment Sequence	Period 1	Period 2	Period 3	Period 4
	Week 1	Week 2	Week 3	Week 4
A (n=21)	Placebo	JZP-110 75 mg	JZP-110 150 mg	JZP-110 300 mg
B (n=21)	JZP-110 75 mg	JZP-110 150 mg	JZP-110 300 mg	Placebo
C (n=7)	Placebo	Placebo	Placebo	Placebo

[figure not shown]
During the first 6 days of each treatment period, subjects will take once-daily, oral doses of study drug (75, 150, or 300 mg JZP-110, or placebo) with water at home.

On the last day of each treatment period (i.e., Days 7, 14, 21, and 28), subjects will take their usual PD medications and sleep medications allowed by the protocol as per their usual schedule, and return to the study center where they will take their dose of study drug for that day and undergo assessments for efficacy and safety and tolerability (Visits 3, 4, 5, and 6; see Section 3.5 for the complete schedule of events). Pending the investigator's assessment of safety and tolerability, subjects will proceed to the next treatment period. Subjects will receive their last dose of study drug at Visit 6 (Day 28) prior to the Week 4 visit assessments. Subjects will return for a Safety Follow-up visit (Visit 7) approximately 7 days after the last dose of study drug for follow-up safety assessments. Unless there are outstanding safety issues that require additional follow-up, subjects will be discharged from the study at the Safety Follow-up visit (Visit 7).

The schema of the study is represented in Figure 1.

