#### 16.1.5. SENSITIVITY ANALYSIS OF KEY EFFICACY ENDPOINT

- **Sensitivity to carry-over effect from the end of period 3 to end of period 4 in Sequence B** (i.e., from JZP-110 300 mg to placebo): ESS total score observed values at end of treatment period for Period 3 and end of treatment for Period 4 for subjects randomized into Sequence B as well as the change from Baseline to each end of the treatment period will be summarized using descriptive statistics by treatment group based on the mITT.

The key efficacy analysis will be repeated adjusting the model for carry-over effect of Period 3 on Period 4, by adding an effect-type coding variable for the 4 treatment groups representing the residual treatment effect of the treatment taken during the previous period as fixed effects (Kuehl, 2000):

Treatment Group	Residual effect of JZP-110 300 mg, x
JZP-110 75 mg	0
JZP-110 150mg	0
JZP-110 300 mg	1
Placebo	-1

In other words, if a subject is randomized to Sequence A (i.e., placebo, JZP-110 75 mg, JZP-110 150 mg, and JZP-110 300 mg), the variable x will be set to the following on Period 4 subject record to represent the treatment group with which the subject was treated during the previous period (i.e., JZP-110 150 mg): x = 0. If a subject is randomized to Sequence B (i.e., JZP-110 75 mg, JZP-110 150 mg, JZP-110 300 mg, and placebo), the variable x will be set to the following on Period 4 subject record to represent the treatment group with which the subject was treated during the previous period (i.e., JZP-110 300 mg): x = 1. Finally, if a subject is randomized to Sequence C (i.e., placebo, placebo, placebo, and placebo), the variable x will be set to the following on Period 4 subject record to represent the treatment group with which the subject was treated during the previous period (i.e., placebo): x = -1.

Log Likelihood and degrees of freedom for each model (adjusted and not adjusted for carry-over effect) will be presented. To assess the significance of the carry-over effect, a likelihood ratio test will be performed as follows: the difference of the ‘-2 residual likelihood fit statistic’ (-2logL) between the 2 models (i.e., -2logL of model no adjusted - -2log L of adjusted model) will be tested using a Chi-square test at 0.05 alpha level with a degree of freedom defined as the difference between degrees of freedom of model adjusting for carryover effect minus degrees of freedom of model not adjusting for carryover effect.

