Should the carryover effect be statistically significant, the key efficacy analysis will be repeated, but excluding period 4 data of subjects randomized to Sequence B.

- **Sensitivity to carry-over effect from the end of period 4 to safety follow-up period in Sequence A** (i.e., from JZP-110 300 mg to not treated with neither JZP-110 nor placebo): Observed values at end of treatment period for period 4 and end of safety follow-up period for subjects randomized into Sequence A as well as change from Baseline in ESS total score to the end of each period will be summarized using descriptive statistics by treatment group based on the mITT. No statistical inferences will be performed.
- **Sensitivity to treatment-by-sequence interaction:** Given the study design, the treatment-by-sequence interaction is aliased with the period effect included in the main model. Hence, p-value for the period effect obtained from the primary analysis of the key efficacy endpoint will be provided.

- **Sensitivity to analysis population:**
  - The key efficacy analysis will be repeated based on the EFF.
  - The key efficacy analysis will be repeated based on the PP.

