## 17.1. ADVERSE EVENTS

Adverse events will be coded to SOC and PT using the MedDRA dictionary (version 18.0) and will be classified as follows:

- **Prior AEs** are defined as AEs that started on or after the signature of the informed consent but prior to the first dose of study drug (i.e., first dose in Period 1) and have not worsened in severity on or after the first dose of study drug;
- **Treatment-emergent adverse events (TEAEs)** are defined as any AEs that started or worsened in severity on or after the first dose of study drug;

Only TEAEs will be summarized; listings will include all AEs (see APPENDIX 1 for handling of partial dates for AEs). AEs will be reported under the treatment group being received when AE first occurs/worsens. Should an AE with a partially missing onset date can be assigned to more than one treatment group, it will be reported under the active treatment group with the lowest dose. For TEAEs that started during the safety follow-up period, TEAEs will be attributed to the last treatment group received in the study.

An overall summary of number and percentage of subjects within each of the categories described in the following subsections (e.g., all TEAEs, SAEs, AEs leading to discontinuation of study drug, etc.) will be provided. A similar overall summary will be presented for the subset of TEAEs that started during the safety follow-up period.

For TEAEs summarized by SOC and PT, SOC will be sorted in alphabetical order and the PTs within each SOC will be sorted in descending frequency order for the pooled JZP-110 treatment group. For PT only tables, incidence will be sorted similarly to the PTs in the summaries by SOC and PT.

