### PRESENTATION OF TREATMENT GROUPS

For outputs where Treatment Sequence will be represented, sequence will be presented as follows and in the order indicated:

Treatment Sequence	For Tables, Figures, and Listings
Sequence A	Placebo/JZP-110 75mg/JZP-110 150mg/ JZP-110 300mg
Sequence B	JZP-110 75mg/JZP-110 150mg/ JZP-110 300mg/Placebo
Sequence C	Placebo/Placebo/Placebo/Placebo

For outputs where treatment groups will be represented, group will be presented as follows and in the order indicated:

Treatment Group	For Tables, Figures, and Listings
JZP-110 75 mg	JZP-110 75 mg
JZP-110 150 mg	JZP-110 150 mg
JZP-110 300 mg	JZP-110 300 mg
JZP-110 pooled	JZP-110 Pooled
Placebo	Placebo

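### New AEs in the first week after 300 mg count under 300 mg in Sequence A but under placebo in Sequence B, and no AE summary described in the SAP sets the two weeks side by side

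*SAP*

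**What the plan says.** SAP 17.1 has two attribution rules. During treatment, "AEs will be reported under the treatment group being received when AE first occurs/worsens". After treatment, "For TEAEs that started during the safety follow-up period, TEAEs will be attributed to the last treatment group received in the study".

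The sequence orders are in SAP Appendix 2. Sequence A is "Placebo/JZP-110 75mg/JZP-110 150mg/ JZP-110 300mg" and Sequence B is "JZP-110 75mg/JZP-110 150mg/ JZP-110 300mg/Placebo". Protocol 3.2 states that "a placebo washout between each treatment period was not included". SAP 3.1 places the Safety Follow-up visit "approximately 7 days after the last dose of study drug for follow-up safety assessments", so follow-up lasts about as long as a treatment period.

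SAP 17 presents safety by treatment group, pooled over sequence and period, and also shows placebo by sequence, pooled over period. SAP 17.1 adds an overall summary of TEAEs that start in follow-up. Safety is the primary objective and is described without inference (Protocol 9.2).

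For ESS, SAP 16.1.5 looks separately at both post-300 mg weeks: "Sensitivity to carry-over effect from the end of period 3 to end of period 4 in Sequence B", and, for Sequence A, the move "from JZP-110 300 mg to not treated with neither JZP-110 nor placebo".

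**The concern.** Sequence A subjects who complete take no active drug in about Days 29 to 35. Sequence B subjects take none in Days 22 to 28. In both cases this is the first week after the last 300 mg dose. A new or worsening AE in that week is a 300 mg event in one sequence and a placebo event in the other.

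If stopping the top dose causes AEs, the pooled 300 mg and placebo columns both rise, and the difference between them shows little of it. The placebo column would contain events that follow 300 mg, and the 300 mg column would hold only about half of them. Time at risk is a separate matter: a rate per week would not correct the labels. So are AEs that persist from one period to the next, because the concern here is new onset or worsening.

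**Working it through.** **Inputs.** Allocation 3:3:1 of 49, and 40 completers: 34 in Sequences A and B together (17 each) and up to 6 in C (SAP 3.4). Safety subjects are classified by treatment received (SAP 5.5), and each subject counts once per category (SAP 17). The column denominators below follow from those rules; the SAP does not print them.

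**The plan's own figures.** 49 × 3/7 = 21, 49 × 3/7 = 21 and 49 × 1/7 = 7; 17 + 17 + 6 = 40. These agree with SAP 3.4.

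**Formula.** Let q be the added probability of a new AE in the week after the last 300 mg dose, taken as equal in Sequences A and B. The documents give no value for it.

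- Gain in the 300 mg column = q × (subjects whose post-300 mg week is credited to 300 mg) / (subjects who received 300 mg).
- Gain in the placebo column = q × (subjects whose post-300 mg week is credited to placebo) / (subjects who received placebo).
- Share offset = placebo gain / 300 mg gain.

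A Sequence B subject who stops on 300 mg never reaches placebo, so follow-up AEs in that subject go to 300 mg.

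| Case | 300 mg gain | Placebo gain | Difference | Share offset |
|---|---|---|---|---|
| Planned, 21/21/7 | 21/42 = 0.500q | 21/49 = 0.429q | 0.071q | 85.7% |
| Completers, 17/17/6 | 17/34 = 0.500q | 17/40 = 0.425q | 0.075q | 85.0% |
| 1 of 21 in B stops on 300 mg (assumed) | 22/42 = 0.524q | 20/48 = 0.417q | 0.107q | 80% |
| 2 of 21 (assumed) | 23/42 = 0.548q | 19/47 = 0.404q | 0.143q | 74% |
| 4 of 21 (assumed) | 25/42 = 0.595q | 17/45 = 0.378q | 0.217q | 63% |
| 4 in each of A and B leave before 300 mg (assumed) | 17/34 = 0.500q | 17/45 = 0.378q | 0.122q | 76% |

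**Illustration.** With planned numbers and q = 20% (assumed), the 300 mg column rises by 10.0 points, placebo by 8.6 points, and the difference by 1.4 points.

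**Background AEs.** Let b be a weekly background AE probability, independent across weeks. The affected 300 mg cell (Sequence A, Period 4 plus follow-up) and the affected placebo cell (Sequence B, Period 4 plus follow-up) each span two weeks. Each subject-level increment is therefore (1 − b)q, and the factor cancels in the ratio. The planned share stays at 85.7% for b from 5% to 30% (assumed).

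**What the planned splits recover.**

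- Sequence A placebo is Period 1 only for completers, and Sequence C is placebo throughout. Both are already shown separately.
- Sequence B placebo merges Period 4 with that sequence's own follow-up week: about 14 days, against 7 for Sequence A placebo. A higher figure could reflect a stopping effect or longer observation.
- The follow-up summary covers the Sequence A week but omits Sequence B Period 4, and no SOC or PT breakdown is stated for it.
- The tables by SOC and PT, severity and relationship (SAP 17.1.1) keep follow-up onsets within the 300 mg column.

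**The case against.** The strongest reply is that much of this is already covered. The placebo-by-sequence display applies to safety outputs generally, so a drug-free reference (Sequence A placebo and Sequence C) is already planned, with Sequence B placebo beside it. Follow-up TEAEs get an overall summary. All AEs are listed with sequence and dose, and about 17 Sequence A completers can be read case by case. Treatment at onset is the protocol's own rule (Protocol 9.13.1), and follow-up needed some convention because no treatment is being taken. All of this stands. It narrows the gap to the one described above.

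Three stronger readings are tempting, and the documents do not support them.

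- **That a stopping effect exists and is being hidden.** No such effect is reported. Protocol 1 and 1.2.1 state no rebound hypersomnia (the cited basis is rodent), Protocol 1.3.1 gives a half-life of 5 to 7.6 hours, and Protocol 3.2 reports no carryover in the earlier narcolepsy crossover. None of these proves that q is zero, but none gives it a value either.
- **That the AE rules contradict SAP 16.1.5.** That section holds sensitivity analyses. The primary ESS model in SAP 16.1.4 also keeps Sequence B Period 4 as placebo, and it leaves follow-up out.
- **That the dose and placebo columns should be replaced.** A placebo column from Sequence A Period 1 and Sequence C would have 23 completers instead of 40, and 17 of the 23 (74%) would contribute Week 1 only. Limiting the main 300 mg column to on-treatment onset would remove delayed reactions from it.

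The two weeks are also not identical: Sequence B takes blinded capsules, while Sequence A knowingly takes none. Reporting may differ, which is a reason to show them separately as well as combined.

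**Conclusion.** The point holds as a gap in presentation. The two rules in SAP 17.1 give the first week after 300 mg opposite labels in Sequences A and B. About 85% of the increment that a stopping effect would add to the 300 mg column is then matched in the pooled placebo column.

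That percentage refers to the column's increment, not to q. If both weeks were credited to 300 mg, the difference would carry 1.00q; under the SAP rules it carries 0.071q to 0.075q. The figure assumes the same q in both sequences and that Sequence B subjects go on to Period 4. It falls to about 80% to 63% if 1 to 4 of 21 stop on 300 mg.

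Safety is descriptive and no test or decision rule uses this difference, so nothing formal is invalidated. What is missing is a summary in which a stopping effect, if there is one, could be seen by preferred term. The table shells are not among the documents reviewed, so this rests on the SAP text. It is a cheap improvement to the analysis of the primary objective.

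**What to change.** Keep the planned AE tables and attribution rules. Add to SAP 17.1 one supplementary summary, by SOC and PT, of TEAEs with onset or worsening in the 7 days after the last 300 mg dose:

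- columns for Sequence A follow-up, Sequence B Period 4, and the follow-up of subjects who stop early on 300 mg, shown separately and combined;
- subjects entering that week as the denominator;
- beside these, 300 mg TEAEs limited to on-treatment onset;
- the Sequence A (Period 1) and Sequence C placebo columns for reference.

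The cost is a paragraph of SAP text and one table. No new data are needed for completers, since AEs are recorded to the final visit (Protocol 6.14.1.5); for early stoppers, coverage depends on their returning for follow-up. The limits should be stated in a footnote: small groups, a placebo reference that is mostly Week 1, and capsules taken in that week in Sequence B but not in Sequence A.

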### 17.1.1. ALL TEAEs

Incidence of TEAEs will be presented by SOC and PT. If a subject reports a TEAE more than once within a SOC or PT, the TEAE will be reported only once for that SOC or PT. Incidence of TEAEs will be similarly presented by PT only.

Incidence of TEAEs by SOC and PT will also be presented by maximum severity and relationship to study drug.

#### 17.1.1.1. SEVERITY

Severity, as determined by the Investigator, will be classed as mild, moderate, severe, life-threatening or fatal. If a subject reports a TEAE more than once within a SOC or PT, the AE with the greatest severity will be used in the corresponding severity summaries.

#### 17.1.1.2. RELATIONSHIP TO STUDY DRUG

Relationship, as indicated by the Investigator, will be classed as “not related” or “related” (i.e. related or suspected to be related) to study drug. If a subject reports the same AE more than once within a SOC or

PT, the AE with the greatest case relationship to study drug will be used in the corresponding relationship summaries.

### **17.1.2. ADVERSE EVENTS WITH AN OUTCOME OF DEATH**

Incidence of AEs with an outcome of death will be summarized by SOC and PT. Generally, only one AE has an outcome of death corresponding to the subject's primary cause of death. In the event that more than one AE has an outcome of death for a subject, the subject will be counted only once within a SOC or PT.

### **17.1.3. SERIOUS ADVERSE EVENTS**

The incidence of SAEs will be summarized by SOC and PT. If a subject reports a SAE more than once within a SOC or PT, the SAE will be reported only once for that SOC or PT.

A listing including all SAEs will be provided.

### **17.1.4. TEAEs LEADING TO DISCONTINUATION OF STUDY DRUG AND/OR TO WITHDRAWAL FROM STUDY**

The incidence of TEAEs leading to permanent discontinuation of study drug and/or to withdrawal from study will be summarized together by SOC and PT. Generally, only one AE has an action taken of 'drug withdrawn' corresponding to subject's primary reason for discontinuation from study drug due to an AE. In the event that more than one AE has an action taken of 'drug withdrawn' for a subject, subject will count only once within a SOC or PT.

A listing including all TEAEs leading to permanent discontinuation of study drug and/or to withdrawal from study will be provided.

## **17.2. LABORATORY EVALUATIONS**

[figure not shown]
Laboratory results will be reported in SI Units.

The following summaries will be provided based on the SAF for the hematology, serum chemistry, and urinalysis data (refer to APPENDIX 3 for the list of laboratory parameters to be included in the summaries):

- Observed and change from Baseline by visit for quantitative (continuous) measurements
- Observed by visit for qualitative (categorical) measurements

A listing of subjects with abnormal value(s) according to normal range criteria (refer to 17.2.1) will be provided.

All laboratory results, including pregnancy test, urine drug screen, and alcohol breath test, will be presented in subject data listings.

### 17.2.1. LABORATORY STANDARD REFERENCE RANGES AND MARKEDLY ABNORMAL CRITERIA

Quantitative laboratory measurements will be compared with the relevant laboratory reference ranges in SI units and categorized as:

- Low: result < LLN
- Normal: result within the laboratory normal reference range (upper and lower limit included)
- High: result > ULN

[figure not shown]
### 17.3. ECG EVALUATIONS

The following ECG parameters will be reported for this study based on core laboratory values:

- HR (beats per minute [bpm])
- RR interval (msec)
- PR interval (msec)
- QRS interval (msec)
- QT interval (msec)
- QT Fridericia's correction (QTcF) interval (msec) [derived]
- QT Bazett's correction (QTcB) interval (msec) [derived]
- Overall evaluation of ECG:
  - Normal
  - Abnormal, not clinically significant
  - Abnormal, clinically significant

The following summaries will be provided based on SAF for ECG data:

- Observed values and change from Baseline to end of period post-dose timepoint (for quantitative measurements)
- Observed values and change from end of period pre-dose timepoint to end of period post-dose timepoint (for quantitative measurements)
- Incidence of markedly abnormal criteria from Baseline to end of period post-dose timepoint (refer to Section 17.3.2 for details) by gender
- Incidence of markedly abnormal criteria from end of period pre-dose timepoint to end of period post-dose timepoint (refer to Section 17.3.2 for details) by gender
- Shift from Baseline to end of period post-dose timepoint in ECG overall evaluation by gender
- Shift from end of period pre-dose timepoint to end of period post-dose timepoint in ECG overall evaluation by gender

- Incidence of subjects for which their ECG overall evaluation improved, remained unchanged or worsened from Baseline to end of period post-dose timepoint by gender
- Incidence of subjects for which their ECG overall evaluation improved, remained unchanged or worsened from the end of period pre-dose timepoint to the end of period post-dose timepoint by gender
- Incidence of subjects with at least one ECG diagnosis by diagnosis category (i.e., rate/rhythm, conduction abnormalities, changes in ST segment, axis, chamber enlargement, myocardial infarction, and miscellaneous) and diagnosis by visit, timepoint, and gender

The following listings will be provided:

- Listing of subjects with any observed QT, QTcB, or QTcF values >450 msec and/or change from Baseline in QT, QTcB, or QTcF >30 msec
- Listing of subjects with any abnormal ECG overall evaluation

The following figures will be provided:

- Line plot of mean observed values across visit by sequence and treatment group;

[figure not shown]

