- Approximately 6 hours after dosing, obtain a 12-lead ECG after the subject has been resting supine for at least 5 minutes.

- [Optional Assessment] If feasible, approximately 7 hours after dosing, initiate the fourth trial of the MWT.
- Document any AEs that occurred since the last visit.
- The safety findings will be reviewed by the investigator, who will decide whether or not to proceed to the next dose.
- Dispense study drug and instruct subject on the daily dose administration to begin on the following morning.
- Complete drug accountability.
- Schedule the next return clinic visit.

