- Administer the C-SSRS Since Last Visit Version and record the results.
- Approximately 2 hours after dosing, obtain vital signs (systolic and diastolic blood pressure [seated and standing] and pulse rate [seated and standing]), including at least 2 sets of blood pressure and pulse rate measurements in the seated position after the subject has been resting and seated for at least 5 minutes. Next, standing blood pressure and pulse rate should be taken at 1 and 3 minutes after the subject has been standing.
- Approximately 2 hours after dosing, 12-lead ECG after the subject has been resting supine for at least 5 minutes.
- Complete the CGIc.
- Administer the MDS-UPDRS (Parts III and IV). When feasible, the MDS-UPDRS (Parts III and IV) is to be performed at approximately the same time for each subsequent visit while the subject is in the “on” state.
- Document any AEs that occurred since the last visit.
- The safety findings will be reviewed by the investigator, who will decide whether or not to proceed to the next dose.
- Dispense study drug and instruct subject on the daily dose administration to begin on the following morning.

- Complete drug accountability.
- Schedule the next return clinic visit.

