### 9.13.4 12-Lead Electrocardiograms

Electrocardiogram intervals and durations will be reviewed for notable abnormalities, and clinically notable abnormalities and findings considered to be clinically significant will be listed. The number and percent of subjects who have a clinically notable ECG interval abnormality or other clinically significant ECG finding will be summarized. A listing of abnormal ECG values will also be provided. Detailed ECG value analyses and the algorithms to derive variables for the clinically significant changes will be specified in the Statistical Analysis Plan.

Electrocardiogram parameter values (HR, RR, PR, QRS, QT, and QT corrected with Fridericia's formula [QTcF]) will be summarized at baseline, at each postbaseline visit, and within each visit across time by treatment group (dose) and by sequence. The number and percentage of subjects with QT and QTcF values falling within or outside of normal ranges will be summarized by treatment (dose) groups and by sequence. The number and percentage

of subjects with other clinically significant ECG findings will also be summarized at each postbaseline time point by treatment (dose) and by sequence group.

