### 9.15 Subgroup Analyses

Exploratory analyses of safety and efficacy will be conducted in subgroups of subjects including but not limited to disease severity (by Hoehn and Yahr stage), treatment with levodopa, dopamine agonists, or a combination of dopamine agonist with levodopa. As sensitivity analyses, efficacy and exploratory analyses may be reported separately for Group 1 and Group 2.

JZP-110

Clinical Trial Protocol: JZP166-201 Amendment 2

---

Jazz Pharmaceuticals

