### **3.6. CHANGES TO ANALYSIS FROM PROTOCOL**

Changes to planned analysis from protocol are:

- The modified Intent-to-Treat (mITT) analysis population is now defined as all randomized subjects who received at least one dose of study drug and have a Baseline and at least one post-Baseline efficacy assessment (refer to Section 5.2) while it was defined as follows in the protocol: all subjects who were randomized, received at least one dose of study medication and have baseline and at least one post-baseline evaluation of ESS;
- When computing the ESS total score, missing ESS item(s) will be imputed by the mean of the non-missing items only if only one or two ESS items are missing. Should three items or more be missing, the ESS total score will not be computed (refer to Section 16.1.1);
- Similarly, imputation techniques for missing MDS-UPDRS Part III individual scores when computing the MDS-UPDRS Part III total score are now planned to be done (refer to Section 16.2.1.2);
- The main analysis of each efficacy endpoint will be done based on the mITT population instead of the efficacy (EFF) population. Sensitivity analysis will be performed based on the EFF;
- Period will be used in the main model instead of the treatment-by-sequence interaction;
- Summaries by sequence will not be presented for the vital signs and electrocardiogram (ECG) endpoints, with the exception of the placebo treatment group for which summaries further broken down by sequence will be presented;
- No subgroup analyses will be conducted by disease severity, treatment with levodopa and treatment with a combination of dopamine agonists and levodopa;
- Non-compartmental PK analysis will be based on multiple dosing as described in Section 18.3
- Numbers and percentage of subjects with abnormal laboratory values post-baseline will not be tabulated by treatment group; only a listing of subjects with abnormal laboratory values will be provided

[figure not shown]

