### 17. SAFETY OUTCOMES

All outputs for safety outcomes will be based on the SAF and, unless otherwise specified, presented by treatment group (JZP-110 75 mg, JZP-110 150 mg, JZP-110 300 mg, and placebo), regardless of the sequence and period. Summaries will also be presented for the pooled JZP-110 treatment groups, when applicable (i.e., incidences and shifts from Baseline), as well as by sequence for Placebo, but regardless of the period.

For subjects who received Sequence C, the following rules will be followed to compute the descriptive statistics, incidences and shifts from Baseline:

- For descriptive statistics, the average of the non-missing values collected at the end of each treatment period will be used;
- For incidences, each subject will be counted only once for each category;
- For shifts from Baseline, the worst value among the non-missing values collected at the end of each treatment period will be used.

For the summaries on the pooled JZP-110 group, the same rules than for the subjects who received Sequence C will be followed for the incidences and shifts from Baseline.

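### Most ECG summaries use one unnamed post-dose timepoint, although the only scheduled post-dose ECG is at about 6 h in Group 1 and about 2 h in Group 2

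*SAP*

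**What the plan says.** At Visits 3 to 6 each Group has a pre-dose ECG and one post-dose ECG, but at different hours.

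- Group 1 (protocol 7.2.2, Appendix 3): "Approximately 6 hours after dosing, obtain a 12-lead ECG after the subject has been resting supine for at least 5 minutes".
- Group 2 (protocol 7.3.2, Appendix 6): "Approximately 2 hours after dosing, 12-lead ECG after the subject has been resting supine for at least 5 minutes".

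SAP 17.3 gives no hour. Its first summary is "Observed values and change from Baseline to end of period post-dose timepoint (for quantitative measurements", and the change from pre-dose, the markedly abnormal incidence, the shifts and the improved/unchanged/worsened counts refer to the same post-dose point. SAP 17 says that safety outputs are "presented by treatment group (JZP-110 75 mg, JZP-110 150 mg, JZP-110 300 mg, and placebo), regardless of the sequence and period"; Group is not a factor. Under SAP 6, Group number appears in listings.

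Two outputs in SAP 17.3 are different. ECG diagnoses are tabulated by category "and diagnosis by visit, timepoint, and gender", and subjects with high QT/QTc values or large QT/QTc increases are listed individually.

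Protocol 9.13.4 planned that ECG parameters "will be summarized at baseline, at each postbaseline visit, and within each visit across time by treatment group (dose) and by sequence". The only ECG change declared in SAP 3.6 is "Summaries by sequence will not be presented for the vital signs and electrocardiogram (ECG) endpoints", with an exception for placebo. Protocol 9.15 allows a split by Group only as an option, and not for safety: "As sensitivity analyses, efficacy and exploratory analyses may be reported separately for Group 1 and Group 2".

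**The concern.** Safety and tolerability is the primary objective, and protocol 9.8 names the 12-lead ECG among its components. Protocol 1.3.1 gives a Tmax of 1.3 to 3.0 h and a half-life of 5 to 7.6 h, so a 2 h ECG is near peak exposure and a 6 h ECG is usually well past it. One column that combines the two describes neither, and any effect that follows concentration would look smaller than it is at 2 h. The threshold counts in SAP 17.3.2 (QT/QTc above 450, 480 or 500 msec; increases above 30 or 60 msec) are exposed to the same problem, because a 6 h ECG is less likely to catch a peak-related exceedance.

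The SAP handles seated blood pressure and pulse differently. SAP 17.4.2 summarises each post-dose timepoint and matches several of them in time to baseline. ECG, which includes heart rate, gets neither.

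**Working it through.** The documents give no ECG effect size, power or precision figure to reproduce. The check therefore covers the schedule and the exposure that it implies.

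**Clock times in the example schedules (protocol Appendices 2, 3, 5 and 6)**

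| | Baseline ECG | Pre-dose ECG | Post-dose ECG |
|---|---|---|---|
| Group 1 | about 8:00 (or the day before) | about 8:00 | about 15:00 |
| Group 2 | about 11:00 | about 8:00 | about 11:00 |

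Change from Baseline is clock-matched only in Group 2. Change from pre-dose spans about 7 h in Group 1 and 3 h in Group 2, so it is matched in neither. These are sample schedules that sites may shift.

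**Concentration at 6 h relative to 2 h**

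Inputs: Tmax 1.3 to 3.0 h and half-life 5 to 7.6 h (protocol 1.3.1); once-daily dosing, so a 24 h interval.

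One-compartment oral model at steady state: C(t) is proportional to e^(-kt)/(1 - e^(-24k)) - e^(-ka·t)/(1 - e^(-24ka)), where k = ln 2 / half-life and ka is set so that the peak falls at Tmax.

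| Half-life | Tmax | k | ka | C(6)/C(2) |
|---|---|---|---|---|
| 5 h | 1.3 h | 0.139 | 2.26 | 0.58 |
| 5 h | 3.0 h | 0.139 | 0.63 | 0.85 |
| 7.6 h | 1.3 h | 0.091 | 2.57 | 0.70 |
| 7.6 h | 3.0 h | 0.091 | 0.76 | 0.89 |

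Worked example, first row: C(2) = 0.758/0.964 - 0.011 = 0.775; C(6) = 0.435/0.964 - 0.000 = 0.452; ratio 0.58.

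The range is 58-89%. If Tmax is instead matched to a single-dose curve and the ratio is then read at steady state, the top of the range is 86%.

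**Pooled mean relative to the 2 h effect**

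Let r = C(6)/C(2), and let s be the share of subjects in Group 1. If the effect is proportional to concentration, pooled/2 h effect = 1 - s(1 - r). The documents do not give s, so it is varied, with r = 0.582 and r = 0.892.

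| s (assumed) | r = 0.582 | r = 0.892 |
|---|---|---|
| 25% | 1 - 0.25 × 0.418 = 0.90 | 1 - 0.25 × 0.108 = 0.97 |
| 50% | 1 - 0.50 × 0.418 = 0.79 | 1 - 0.50 × 0.108 = 0.95 |
| 75% | 1 - 0.75 × 0.418 = 0.69 | 1 - 0.75 × 0.108 = 0.92 |

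**Effect on the dose-placebo contrast**

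A subject in Sequence A or B stays in one Group, so the scheduled ECG hour is the same on placebo and on each dose. The within-subject contrast is averaged over time after dose and is not distorted by it. Sequence C contributes to the placebo column only, and randomization is not stratified by Group. The mix of hours in the placebo and active columns can therefore differ somewhat by chance.

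**The case against.** Several points on the other side stand.

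- A reader might infer that every ECG output is pooled. It is not: the diagnosis table names timepoint, and the QT/QTc listings show individual values that can be traced to Group.
- A reader might infer that the SAP orders the hours to be combined. It does not; the pooling is by omission. SAP 8 leaves table format and content to shells that are not in these documents and might separate the hours.
- A reader might infer that the drug-placebo comparison is biased, or that time of day confounds it. In Sequences A and B the crossover holds the scheduled hour fixed, so clock effects largely cancel there. They matter when change from Baseline is read alone.
- Simple decay from 2 h to 6 h, 2^(-4/5) = 0.57 to 2^(-4/7.6) = 0.69, suggests a larger loss. It ignores continuing absorption when Tmax is later than 2 h, so the wider range above is the one to use.
- The practical stakes are modest. Protocol 1.3.3 reports no effect on ECG intervals in the earlier 12-week narcolepsy study, protocol 1.3.6 reports no clinically significant ECG effect across 690 treated subjects, and protocol 9.2 keeps safety descriptive.
- Protocol 9.13.4 does not clearly demand a split by hour, since each visit has one pre-dose and one post-dose ECG and the SAP reports the change between them.

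None of this supplies the missing hour in SAP 17.3. Earlier data without an ECG signal are also not a reason to blur the exposure at which a new population is examined.

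**Conclusion.** The point holds as a partial attenuation and a gap in reporting. Followed as written, SAP 17.3 mixes near-peak and later ECGs in most of its summaries. The pooled mean would show about 79-95% of the 2 h effect at an assumed 50% Group 1 share, about 90-97% at 25%, and about 69-92% at 75%.

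These figures assume a one-compartment model, the protocol's Tmax and half-life ranges, and an effect proportional to concentration. The documents do not establish the last of these, and they do not give the Group mix.

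The documents do not support a claim of bias in the within-subject contrast, and no trial conclusion is shown to depend on the pooling. Reporting by hour is an inexpensive improvement to a named part of the primary objective. It cannot create a near-peak ECG for Group 1, because none is scheduled.

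**What to change.** In SAP 17.3:

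- Present the quantitative ECG summaries, the markedly abnormal incidence and the shifts by scheduled post-dose hour (2 h, 6 h, and any other hour used before Amendment 2), each next to placebo at the same hour.
- Define the columns by hour and not by Group, because the ECG times for subjects enrolled before Amendment 2 are not given here.
- Keep the pooled table, labelled as any post-dose ECG.
- Footnote that Group 1 has no near-peak ECG and that its change from Baseline is not clock-matched in the example schedules.
- Do not make Group 2 the headline result: Group depends on site capability and subject choice.
- Reconcile SAP 17.3 and 3.6 with protocol 9.13.4, either by reporting within each visit across time or by declaring the change.

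The cost is SAP wording and extra columns; no new ECGs are needed. Only 21 + 21 = 42 subjects are planned for the sequences that contain active drug, so numbers per column will be small and the by-hour incidence tables may have to drop the gender split. That is acceptable in a descriptive analysis.
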